**CONTRACEPTIVESa ALLOWED DURING THE STUDY INCLUDE:****Sexual abstinence**

*Sexual abstinence is considered a highly effective method only if defined as refraining from reproductive sexual intercourse during the entire period of risk associated with the study intervention. The reliability of sexual abstinence needs to be evaluated in relation to the duration of the study and the preferred and usual lifestyle of the participant.*

**Effective Methodsd That Are Not Considered Highly Effective Failure rate of  $\geq 1\%$  per year when used consistently and correctly.**

- Progestogen-only oral hormonal contraception where inhibition of ovulation is not the primary mode of action
- Condom with or without spermicide
- Cervical cap, diaphragm, or sponge with spermicide
- A combination of external condom with either cervical cap, diaphragm, or sponge with spermicide (double-barrier methods)c

Note: Periodic abstinence (calendar, symptothermal, postovulation methods), withdrawal (coitus interruptus), spermicides only, and lactational amenorrhea method (LAM) are not acceptable methods of contraception.

- a. Contraceptive should be consistent with local regulations regarding the use of contraceptive methods for those participating in clinical studies.
- b. Failure rate of  $<1\%$  per year when used consistently and correctly. Typical use failure rates differ from those when used consistently and correctly.
- c. If locally required, in accordance with Clinical Trial Facilitation Group (CTFG) guidelines, acceptable contraceptive methods are limited to those which inhibit ovulation as the primary mode of action.
- d. Considered effective, but not highly effective - failure rate of  $\geq 1\%$  per year.

## 10.5. Appendix 5: CDC Working Case Definitions of Pericarditis, Myocarditis, and Myopericarditis Occurring After Receipt of COVID-19 mRNA Vaccines

The CDC Working Case Definitions of probable and confirmed myocarditis, pericarditis, and myopericarditis ([Gargano et al 2021](#)) are provided in [Table 7](#) as guidance.

**Table 7: Case Definitions of Probable and Confirmed Myocarditis, Pericarditis, and Myopericarditis**

Condition	Definition	
Acute myocarditis	Probable case	Confirmed case
	
Presence of <math>\geq 1</math> new or worsening of the following clinical symptomsa
 
 
• Chest pain, pressure, or discomfort
 
• Dyspnea, shortness of breath, or pain with breathing
 
• Palpitations
 
• Syncope
 
	
Presence of <math>\geq 1</math> new or worsening of the following clinical symptomsa
 
 
• Chest pain, pressure, or discomfort
 
• Dyspnea, shortness of breath, or pain with breathing
 
• Palpitations
 
• Syncope
 

	
OR, infants and children aged <math><12</math> years might instead have <math>\geq 2</math> of the following symptoms:
 
 
• Irritability
 
• Vomiting
 
• Poor feeding
 
• Tachypnea
 
• Lethargy
 
	
OR, infants and children aged <math><12</math> years might instead have <math>\geq 2</math> of the following symptoms:
 
 
• Irritability
 
• Vomiting
 
• Poor feeding
 
• Tachypnea
 
• Lethargy
 

	
AND  <math>\geq 1</math> new finding of
 
 
• Troponin level above upper limit of normal (any type of troponin)
 
• Abnormal electrocardiogram (ECG or EKG) or rhythm monitoring findings consistent with myocarditisc
 
• Abnormal cardiac function or wall motion abnormalities on echocardiogram
 
• cMRI findings consistent with myocarditis
 
	
AND  <math>\geq 1</math> new finding of
 
 
• Histopathologic confirmation of myocarditisb
 
• cMRI findings consistent with myocarditis in the presence of troponin level above upper limit of normal (any type of troponin)
 

Condition	Definition	
	AND 
 
• No other identifiable cause of the symptoms and findings
 
	AND 
 
• No other identifiable cause of the symptoms and findings
 

Acute pericarditis d	Presence of $\geq 2$ new or worsening of the following clinical features: 
 
• Acute chest paine
 
• Pericardial rub on exam
 
• New ST-elevation or PR-depression on EKG
 
• New or worsening pericardial effusion on echocardiogram or MRI
 
	
	OR , infants and children aged $<12$ years might instead have $\geq 2$ of the following symptoms: 
 
• Irritability
 
• Vomiting
 
• Poor feeding
 
• Tachypnea
 
• Lethargy
 
	OR , infants and children aged $<12$ years might instead have $\geq 2$ of the following symptoms: 
 
• Irritability
 
• Vomiting
 
• Poor feeding
 
• Tachypnea
 
• Lethargy
 

Myopericarditis	This term may be used for participants who meet criteria for both myocarditis and pericarditis.	

Abbreviations: CDC = Centers for Disease Control and Prevention; CEAC = Cardiac Event Adjudication Committee; cMRI = cardiac magnetic resonance imaging; ECG or EKG = electrocardiogram; MRI = magnetic resonance imaging.

Note: An independent CEAC comprising medically qualified personnel, including cardiologists, will review suspected cases of myocarditis, pericarditis, and myopericarditis to determine if they meet CDC criteria for “probable” or “confirmed” events, ([Gargano et al 2021](#)). The CEAC members will be blinded to study intervention. Details regarding the CEAC composition, responsibilities, procedures, and frequency of data review will be defined in the CEAC charter.

- a. Participants who lack the listed symptoms but who meet other criteria may be classified as subclinical myocarditis (probable or confirmed).
- b. Using the Dallas criteria ([Aretz et al 1987](#)). Autopsy cases may be classified as confirmed clinical myocarditis on the basis of meeting histopathologic criteria if no other identifiable cause.
- c. To meet the ECG or rhythm monitoring criterion, a probable case must include at least one of 1) ST-segment or T-wave abnormalities; 2) Paroxysmal or sustained atrial, supraventricular, or ventricular arrhythmias; or 3) AV nodal conduction delays or intraventricular conduction defects.

Using either the original or the revised Lake Louise criteria.

<https://www.sciencedirect.com/science/article/pii/S0735109718388430?via%3Dihub> external icon

- d. <https://academic.oup.com/eurheartj/article/36/42/2921/2293375> external icon
- e. Typically described as pain made worse by lying down, deep inspiration, or cough, and relieved by sitting up or leaning forward, although other types of chest pain might occur.

Reference: ([Gargano et al 2021](#)).

## 10.6. Appendix 6: Exclusion Criterion 6 – Other Conditions That May Cause Elevated Cardiac Troponin I Levels

In addition to the conditions listed in exclusion criterion #5 ([Section 5.2](#)), other medical conditions that may cause elevated cTnI levels are listed in [Table 8](#).

**Table 8: Other Conditions That May Cause Elevated Cardiac Troponin I Levels**

Infiltrative diseases	

• Amyloidosis

• Sarcoidosis

• Hemochromatosis

Respiratory	

• Chronic lung disease

• Pulmonary embolism with right ventricular dysfunction

Inherited diseases	

• Duchenne muscular dystrophy

Myocardial injury or trauma (within 1 month of Screening)	

• Cardiac surgery

• Chest wall trauma

• Drug toxicity (eg, adriamycin, 5-fluorouracil)

Autoimmune diseases	

• Autoimmune diseases that can cause inflammation or direct damage to the heart

– Systemic lupus erythematosus

– Rheumatoid arthritis

– Scleroderma

– Sarcoidosis

– Polyarteritis nodosa

Miscellaneous	

• Rhabdomyolysis (within 1 month of screening)

## Document History

Version	Date	Description of main modifications
1.0	18 February 2025	Original version per the study protocol dated on 16JUL2024.

## List of Abbreviations

Abbreviation	Definition
AE	Adverse Event
AESI	Adverse Event of Special Interest
AR	Adverse Reaction
BMI	Body Mass Index
CDC	Center For Disease Control
CEAC	Cardiac Event Adjudication Committee
CI	Confidence Interval
CMQ	Customized MedDRA Query
COVID-19	Coronavirus Disease 2019
CRF	Case Report Form
cTnI	Cardiac Troponin I
eCRF	Electronic Case Report Form
eDiary	Electronic Diary
EOS	End of Study
FSH	Follicle-Stimulating Hormone
GCP	Good Clinical Practice
hs-cTnI	High-Sensitivity Cardiac Troponin I
ICF	Informed Consent Form
IM	Intramuscular(ly)
IP	Investigational Product
IRT	Interactive Response Technology
MAAE	Medically Attended Adverse Event
Max	Maximum
MedDRA	Medical Dictionary for Regulatory Activities
Min	Minimum
mRNA	Messenger Ribonucleic Acid
Q1	First Quartile
Q3	Third Quartile
SAE	Serious Adverse Event
SAP	Statistical Analysis Plan
SD	Standard Deviation

Abbreviation	Definition
SMQ	Standardized MedDRA Query
SoA	Schedule of Activities
TEAE	Treatment-Emergent Adverse Event
WHO	World Health Organization

## 1. Introduction

This statistical analysis plan (SAP), which describes the planned analyses for Study mRNA-1273-P404, is based on the most recent approved clinical study protocol (CSP), dated 16-JUL-2024 and case report form (CRF) dated 30-SEP-2024.

This Phase 4 randomized, placebo-controlled, crossover study will assess cardiac troponin I (cTnI) levels after vaccination with mRNA-1273.712 or placebo in individuals 12 through 30 years of age. This study design will allow comparison of cardiac troponin I elevation after mRNA-1273.712 vaccination versus no vaccination.

PPD Biostatistics and programming team, designee of Moderna Biostatistics and Programming department, will perform the statistical analysis of the safety and biomarker data; Statistical Analysis System (SAS) Version 9.4 or higher will be used to generate all statistical outputs (tables, figures, listings, and datasets). The SAP will be finalized and approved prior to the final analysis clinical database lock and treatment unblinding for the study. If the methods in this SAP differ from the methods described in the protocol, the SAP will prevail.

In this document, intervention, injection, and dose are used interchangeably.

## 2. Study Objectives

### 2.1 Primary Objective

To assess cTnI values in participants who received mRNA1273.712 or placebo at Day 4 or Day 32 (3 days after Dose 1 or Dose 2)

### 2.2 Secondary Objectives

- To assess cTnI values in participants who received mRNA1273.712 or placebo at Day 1, Day 29, or Day 57.
- To evaluate the safety of mRNA1273.712 throughout study.

### 2.3 Exploratory Objective

To assess cTnI values in participants who received mRNA-1273.712 or placebo.

## 3. Study Endpoints

### 3.1 Primary Endpoint

Proportion of participants with elevated cTnI level at Day 4 or Day 32 (3 days after Injection 1 or Injection 2).

### 3.2 Secondary Endpoints

- Proportion of participants with elevated cTnI level at Day 1 (baseline).
- Proportion of participants with elevated cTnI level at Day 29 or Day 57 (28 days after Injection 1 or Injection 2).
- Serious adverse events (SAEs), medically-attended adverse events (MAAEs), adverse events of special interest (AESIs), and adverse events (AEs) leading to withdrawal throughout study.

### 3.3 Exploratory Endpoint

cTnI levels at Day 1, Day 4, Day 29, Day 32, and Day 57.

## 4. Study Design

### 4.1. Overall Study Design

This is a Phase 4 study designed as a randomized, observer-blind, placebo-controlled, crossover clinical study to assess cTnI levels after vaccination with the KP.2 variant containing messenger ribonucleic acid mRNA-1273.712 Coronavirus disease 2019 (COVID19) vaccine in individuals 12 through 30 years of age. The study will be conducted at clinical study sites across the United States.

Participants will receive study intervention by intramuscular (IM) injection on Day 1. The study will follow a crossover design and the study intervention sequence will be switched on Day 29. Participants will be followed for approximately 1 month after each injection, for a total study duration of approximately 2 months. Safety assessments throughout the study will include SAEs, MAAEs, AESIs, and AEs leading to withdrawal.

Blood samples will be collected from all participants at pre-injection on the day of each injection, as well as at 3 and 28 days after each injection for assessment of cTnI. To aid interpretation of cTnI assessment, participants will record vigorous physical activities in their eDiary for specific periods during the study (i.e., if an elevated cTnI level is detected during the analysis, the activity data for that participant will be reviewed for correlation of vigorous physical activities with elevated cTnI levels) ([Table 4](#)). Depending on when the study injections or end of study (EOS) is scheduled to be completed, the participant will be asked to complete the eDiary for 4 consecutive days post-Injection 1 (Day 1), 4 consecutive days pre- and post-Injection 2 (Day 29), and 4 consecutive days prior to EOS visit (Day 57), and on the day of the EOS visit. Participants will be encouraged, but not required, to avoid vigorous physical activities, when possible, for 4 days

before and after each study injection. Vigorous physical activities refer to activities that take hard physical effort and make you breathe much harder than normal.

The study will be comprised of 5 scheduled in-clinic visits including a combined Screening and Day 1 Visit. Procedures for Screening and injection/baseline should be performed on the same day (Day 1 Visit) but may be performed on 2 separate days if needed due to extenuating circumstances ([Table 3](#)). This study will be conducted in compliance with the protocol, Good Clinical Practice (GCP), and all applicable regulatory requirements.

### **Study Duration:**

Participants will be in the study for approximately 2 months, which includes:

- Up to 7 days for Screening and Baseline (Day -7 to Day 1)
- Administration of study injection (Day 1 and Day 29)
- Approximately 2 months of follow-up (28 days after each injection)

[figure not shown]
### **Number of Participants:**

Approximately 1000 adolescent and adult (12 through 30 years of age, inclusive) participants will be randomized in a 1:1 ratio (approximately 500 participants in each intervention sequence) to receive either ~~CCI~~  $\mu$ g of mRNA-1273.712 followed by placebo 28 days later (mRNA-1273.712 – placebo [Sequence 1]) or placebo followed by ~~CCI~~  $\mu$ g of mRNA-1273.712 28 days later (placebo – mRNA-1273.712 [Sequence 2]). The interval between the 2 study injections is not expected to introduce any carry-over effects given that troponin elevations are expected to persist for a few days to a couple of weeks, depending on the underlying cause. At least 45% of participants will be enrolled in each of the age groups (12 through 17 years and  $\geq 18$  through 30 years) at clinical study sites across the United States.

### **Study Interventions:**

A ~~CCI~~- $\mu$ g dose of mRNA-1273.712 and placebo, administered IM, in a crossover manner ([Figure 1](#)).

## Figure 1: Study Schema

Abbreviation: EOS = end of study

### 4.2. Sample Size and Randomization

Approximately 1000 participants will be randomized in a 1:1 ratio to one of 2 intervention sequences (approximately 500 participants in each intervention sequence) in this study, to receive **CCI** µg of mRNA-1273.712 followed by placebo 28 days later (mRNA-1273.712 – placebo [Sequence 1]) or to receive placebo followed by **CCI** µg of mRNA-1273.712 28 days later (placebo – mRNA-1273.712 [Sequence 2]). Approximately 1000 participants will receive **CCI** µg of mRNA-1273.712 for Injection 1 or Injection 2, due to the crossover design. Assuming approximately 10% of participants would be excluded from the mRNA-1273.712 group (Injection 1 or Injection 2) in the Evaluable Set due to any reasons (e.g., early dropout, and major protocol deviations that impact key analysis data), the study has more than 90% probability to observe at least 1 participant receiving mRNA-1273.712 (Injection 1 or Injection 2) with an elevated cTnI at a true rate of 0.3%.

Random assignment of participants will use a centralized interactive response technology (IRT), in accordance with pre-generated randomization schedules.

### 4.3. Blinding and Unblinding

This study is observer blind. The Investigator, study staff, study participants, study site monitors, and Sponsor personnel (or its designees) will be blinded to the study intervention administered until study end. Unblinded pharmacy personnel (of limited number) will be assigned to study intervention accountability procedures and will prepare and administer mRNA-1273.712 or

placebo to all participants. Unblinded study site monitors, not involved with other aspects of monitoring, will be assigned as the study intervention accountability monitors.

The study Data Blinding Plan provides details of the blinding/unblinding process and personnel. The study site staff, Investigators, study monitors, and participants will remain blinded until the EOS.

## **5. Analysis Populations**

The following analysis sets are defined: Randomized Set, Safety Set, and Evaluable Set.

### **5.1 Randomization Set**

The Randomization Set consists of all participants who are randomized in the study, regardless of the participants' treatment status in the study. Participants will be included in the intervention sequence to which they are randomized and analyzed accordingly.

### **5.2 Safety Set**

The Safety Set consists of all randomized participants which receive at least one dose of study intervention. Participants will be included in the intervention sequence corresponding to Injection 1 or Injection 2 received. The safety set will be used for all safety analyses. Analysis will be based on the intervention received rather than the intervention they were randomly assigned.

### **5.3 Evaluable Set**

The Evaluable Set consists of all participants in the Safety Set who have no major protocol deviations or conditions/medications that impact critical or key analysis data. This set will be used for biomarker analyses. Analysis will be based on the intervention group/intervention sequence participants received. Major protocol deviations may include deviations of study procedures/assessments, study treatment admin/dispense (including dosing errors), missing endpoint assessments, concomitant medication, or visiting scheduling. Based on the planned dose of ~~CCI~~  $\mu$ g, participants with  $\leq 75\%$  or  $>150\%$  dose level will be excluded from the Evaluable Set.

A few analyses will also use a set called Screen Failed to specifically examine the participants that were screen failures. Participants randomized but not meeting eligibility criteria will also be examined for inclusion/exclusion criteria deviations.

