## 4. STUDY DESIGN

### 4.1. Overall Design

This is a Phase 4 study designed as a randomized, observer-blind, placebo-controlled, crossover clinical study to assess cTnI levels after vaccination with the KP.2 variant-containing mRNA-1273.712 COVID-19 vaccine in individuals 12 through 30 years of age.

The Investigator, study staff, study participants, study site monitors, and Sponsor personnel (or its designees) will be blinded to the study intervention administered until study end. Unblinded pharmacy personnel (of limited number) will be assigned to study intervention accountability procedures and will prepare and administer mRNA-1273.712 or placebo to all participants.

Unblinded study site monitors, not involved with other aspects of monitoring, will be assigned as the study intervention accountability monitors.

Approximately 1000 adolescent and young adult participants (12 through 30 years of age, inclusive, at Screening) will be enrolled and randomized in a 1:1 ratio (approximately 500 participants in each intervention sequence) to receive 2 study interventions (mRNA-1273.712 and placebo), in a crossover design. After each study intervention, the participant will be followed for 28 days. Participants will receive either mRNA-1273.712 ~~cc1~~ µg followed by placebo 28 days later (Sequence 1) or placebo followed by mRNA-1273.712 ~~cc1~~ µg 28 days later (Sequence 2). The interval between the study injections is not expected to introduce any carry-over effects given that troponin elevations are expected to persist for a few days to a couple of weeks, depending on the underlying cause. At least 45% of participants will be enrolled in each of the age groups (12 through 17 years and  $\geq$ 18 through 30 years).

Participants will be followed for approximately 1 month after each study injection, for a total duration of approximately 2 months overall. Safety assessments throughout the study will include SAEs, MAAEs, AESIs, and AEs leading to withdrawal.

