**Table 4: Study Interventions Administered**

Intervention Name	mRNA-1273.712	Placebo
Dose	CCI $\mu$ g	N/A
Dosage Form	Dispersion for injection	Sodium chloride for injection
Route of Administration	IM injection	IM injection

Abbreviations: IM = intramuscular; mRNA = messenger ribonucleic acid; N/A = not applicable.

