### 7.2. Participant Discontinuation/Withdrawal from the Study

- A participant may withdraw from the study at any time at the participant's own request for any reason (or without providing any reason). If a participant chooses to withdraw from the study, the Investigator (or designee) should document the reason for withdrawal in EDC if the participant provides one.
- A participant may be withdrawn at any time at the discretion of the Investigator for safety, behavioral, or compliance reasons.
- At the time of discontinuing from the study, if possible, an early discontinuation visit should be conducted, as shown in the SoA ([Table 1](#)). See the EOS Visit in the SoA for data to be collected at the time of study discontinuation and follow-up and for any further evaluations that need to be completed.
- The participant will be permanently discontinued from the study intervention and the study at that time.
- A participant who withdraws from the study will not be replaced.
- If the participant withdraws consent for disclosure of future information, the Sponsor may retain and continue to use any data collected before such a withdrawal of consent.
- If a participant withdraws from the study, the participant may request destruction of any samples taken and not tested, and the Investigator must document this in the site study records.

- The Sponsor will continue to retain and use all research results that have already been collected for the study evaluation. All biological samples that have already been collected may be retained and analyzed at a later date (or as permitted by local regulations).

From an analysis perspective, a “withdrawal” from the study refers to a situation wherein a participant does not return for the final visit foreseen in the protocol. All data collected until the date of withdrawal or last contact of the participant will be used for the analysis. A participant is considered a “withdrawal” from the study when no study procedure has occurred, no follow-up has been performed, and no further information has been collected for that participant from the date of withdrawal or last contact.

Information relative to the withdrawal will be documented in EDC. The Investigator will document whether the decision to withdraw a participant from the study was made by a participant, or by the Investigator, as well as which of the following possible reasons was responsible for withdrawal:

- SAE (specify)
- Death
- Lost to follow-up

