### **7.3. Lost to Follow-up**

If a participant does not complete a visit, every effort should be made to complete the assessments for that visit within the allotted time window. If a participant still does not complete the visit after all of these efforts, the visit will be classified as missed and all safety requirements of the missed visit will be captured and included in the subsequent visit. The missed study visit will be recorded as a protocol deviation. The participant will continue with subsequent scheduled study visits per their original schedule (ie, relative to their Day 1 Visit).

A participant will be considered lost to follow-up if the participant repeatedly fails to return for scheduled visits and is unable to be contacted by the study site.

The following actions must be taken if a participant fails to return to the clinic for a required study visit:

- The site must attempt to contact the participant and reschedule the missed visit. If contact is made, the participant should be counseled on the importance of maintaining the assigned visit schedule and ascertain whether the participant wishes to and/or should continue in the study.
- Before a participant is deemed lost to follow-up, the Investigator or designee must make every effort to regain contact with the participant (where possible, 3 telephone calls, and if necessary, a certified letter to the participant's last known mailing address or local equivalent methods). These contact attempts should be documented in the participant's source documents.
- If due diligence, as described above, has been completed, the participant will be considered lost to follow-up and discontinued from the study.

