**Table 5: Analysis Sets**

Analysis Set	Description
Randomization Set	All randomized participants.
Safety Set	All randomized participants who receive at least one dose of study intervention. Participants will be included in the intervention group corresponding to Injection 1 or Injection 2 received.
Evaluable Set	All participants in the Safety Set who have no major protocol deviations or conditions/medications that impact critical or key analysis data.

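### The Evaluable Set is defined per participant although the primary troponin comparison is per injection, so a valid 3-day result can be dropped for a reason in the other period or after the draw (minor)

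*SAP*

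**What the plan says.** **Unit of exclusion.** SAP 5.3 defines the Evaluable Set as "all participants in the Safety Set who have no major protocol deviations or conditions/medications that impact critical or key analysis data", and Protocol Table 5 likewise takes Safety Set participants "who have no major protocol deviations or conditions/medications that impact critical or key analysis data". SAP 5.3 assigns this set to the biomarker analyses.

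**Grounds for exclusion.**
- Firm: participants whose dose was at or below 75%, or above 150%, of the planned level fall under the rule that such a "dose level will be excluded from the Evaluable Set". Protocol Table 4 lists placebo as "Sodium chloride for injection" with no dose level, so the rule concerns the vaccine injection.
- Discretionary: major deviations may include "missing endpoint assessments, concomitant medication, or visiting scheduling". Protocol 7.3 adds that "The missed study visit will be recorded as a protocol deviation". Protocol 6.9.3 allows a participant who receives a non-study vaccine after the first injection to be removed from the analyses, without limiting this to later samples.

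**Unit of analysis.** SAP 6.1 and Protocol 9.4.3 build the mRNA-1273.712 and placebo groups by injection, so one participant can count in both. SAP 6.3.1 bases percentages on non-missing troponin results at each timepoint and uses an unpaired interval (Miettinen and Nurminen) for the difference.

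**The concern.** The set is participant-level and the comparison is injection-level. Nothing in SAP 5.3 ties an exclusion to the injection or sample it affects. A Day 4 result could therefore be lost because of a Day 29 dosing error, a missed Day 32 or Day 57 visit, or a vaccine given after the sample was drawn.

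Two things are at stake. Some valid results are discarded. Also, whether a result counts can depend on what happened after it was taken. Only about 3 elevations are expected in the vaccine group at the planning rate, so each result's inclusion should rest on grounds that concern that result.

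**Working it through.** **1. Which results the dose rule removes.** The trigger is the vaccine dose, and the participant's placebo result goes with it.
- Sequence 2 (placebo first): the placebo result is Day 4 and the vaccine is given on Day 29. 29 - 4 = 25, so the sample precedes the dose by about 25 days and cannot have been affected by it.
- Sequence 1 (vaccine first): the vaccine is given on Day 1 and the placebo result is Day 32. 32 - 1 = 31 days later. Protocol 4.1 says "The interval between the study injections is not expected to introduce any carry-over effects", but that describes the planned regimen, so this case is less clear-cut.

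The documents give no frequency of out-of-range doses. At assumed rates of 0.25% to 2%, 1000 × 0.0025 = 2.5 to 1000 × 0.02 = 20 placebo results are lost. At an assumed 0.3% elevation rate these hold 2.5 × 0.003 = 0.0075 to 20 × 0.003 = 0.06 expected elevations.

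**2. The plan's own figure.** Inputs from Protocol 9.6 and SAP 4.2: 1000 vaccine recipients, about 10% excluded, true rate 0.3%.
- n = 1000 × 0.90 = 900, with 900 × 0.003 = 2.7 expected elevations.
- P(at least 1) = 1 - 0.997^900 = 93.3%. The stated probability of more than 90% is reproduced.
- It stays true down to n = 767 (1 - 0.997^767 = 90.02%; n = 766 gives 89.99%), a loss of 23.3%.

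**3. What per-injection evaluability would keep.** The documents give no loss rate per period. Assume equal, independent losses *d* in the two periods. A per-injection set keeps 1000(1 - d) results per group. A participant-level set keeps 1000(1 - d)².

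| Reading of the 10% | d | Per participant | Per injection | P(at least 1) |
|---|---|---|---|---|
| Participant-level loss | 1 - √0.90 = 5.13% | 900 | 1000 × √0.90 ≈ 949 | 93.3% → 94.2% |
| Per-injection loss | 10% | 1000 × 0.90² = 810 | 900 | 91.2% → 93.3% |

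Valid results recovered per group: 949 - 900 = 49 or 900 - 810 = 90. At 0.3% they hold 49 × 0.003 ≈ 0.15 or 90 × 0.003 = 0.27 expected elevations.

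**4. Effect on the intervals.** Illustrative counts (assumed): 3 vaccine elevations and 1 placebo elevation.

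| n per group | Clopper-Pearson 95%, 3/n | Miettinen-Nurminen 95%, 3 vs 1 (percentage points) |
|---|---|---|
| 810 | 0.08% to 1.08% | -0.36 to 0.97 |
| 900 | 0.07% to 0.97% | -0.32 to 0.88 |
| 949 | 0.07% to 0.92% | -0.31 to 0.83 |

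**5. Limit of the model.** Protocol 9.6 names early dropout as one reason for loss. A Sequence 2 participant who leaves before Day 29 has no vaccine result to recover. Dropout also makes the losses in the two periods dependent. The real gain is therefore smaller than in step 3.

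**The case against.** **The text points both ways.** Protocol 9.6 and SAP 4.2 word the 10% as exclusion from the mRNA-1273.712 group, by injection, within the Evaluable Set. SAP 6.3.1 counts only non-missing results and tabulates normal, elevated and missing values by timepoint, so it expects participants with missed samples to stay in the set. This stands as evidence that injection-level exclusion may be intended. The set definition does not carry it out.

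**Most grounds are discretionary.** Missing assessments, scheduling and later vaccines are worded as possibilities. Protocol 7.3 calls a missed visit a deviation, not a major one. SAP 6.2.6 leaves the rules for major deviations to be finalized before lock. This also stands: those rules could settle the discretionary grounds. They would not reopen the dose-level sentence, which is already fixed.

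**Harm is limited.** Exclusion reasons are summarized, all troponin data are listed, and SAP 6.3 repeats the analyses in the Safety Set. The repeat is exploratory, however, and readmits samples that really were affected by a deviation. A participant-level set also helps to keep the same people in both groups, which is a fair reason to prefer it.

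**Stronger readings that the documents do not support.**
- A reader might infer that participants with a cardiac event after vaccination would be dropped, hiding elevations. No passage makes such an event a ground for exclusion.
- A reader might see a contradiction with Protocol 7.2, where "All data collected until the date of withdrawal or last contact of the participant will be used for the analysis". That sentence concerns participants who withdraw and does not govern analysis sets. The Safety Set repeat can use those data.
- A reader might conclude that the sample-size statement fails. It holds under both readings of the 10%.

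**Conclusion.** The point holds as a minor one. The participant-level definition does not match the injection-level comparison. The dose rule, applied as written, removes placebo results that it need not remove, most clearly Day 4 in Sequence 2. For the other grounds the loss is possible rather than certain.

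The gain from changing the rule is at most about one to two percentage points in the probability of seeing an elevation, under assumed equal and independent period losses, and less with dropout. The dose rule alone touches at most about 0.06 expected elevations at the assumed error rates, so any bias from it is negligible. The case for acting is that inclusion should not depend on later or unrelated events, and that the change is cheap. The study's conclusion is not at risk.

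**What to change.** In SAP 5.3, before database lock and unblinding, add an evaluability flag per injection and per timepoint for the intervention-group troponin analyses:

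- Exclude a result only for a major deviation, condition or medication that could affect that sample and occurred before it was drawn. A missed sample or visit in the other period, or anything after the draw, does not exclude it.
- Apply the existing dose-level rule to the results of the injection concerned. State explicitly whether Day 32 in Sequence 1 stays in after an out-of-range vaccine dose, given the protocol's no-carry-over expectation.
- For non-study vaccines, keep samples drawn before the vaccine. Otherwise apply Protocol 6.9.3 by vaccine type as written: its 28-day look-back covers other licensed vaccines, while COVID-19 vaccines have a separate 3-month rule before the first injection.
- Flag Day 29 separately for its two uses (28 days after Injection 1, and before Injection 2).
- Keep the participant-level flag for disposition, demographics and the by-sequence change-from-Day-1 outputs, which span both periods.
- Record the departure from Protocol Table 5 in SAP section 7, which now states that there are no changes.

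Cost: a few sentences and one extra flag per troponin result. The downside is two flags to maintain, and slightly different participants and denominators in the two groups.
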